1.1 List of Tables

Table 1: Objectives, endpoints and statistical considerations	13
Table 2: Planned Efficacy Analyses and Expected Timing	20
Table 3: Operating Characteristics and Power Estimations	21
Table 4: Censoring rules for EFS.	45
Table 5: Estimand Attributes EFS	46
Table 6: Sensitivity analyses for EFS	50
Table 7: Supplementary analysis for EFS	51
Table 8: Estimand Attributes OS	53
Table 9: Censoring rules for PFS.	54
Table 10: Analyses for PFS	54
Table 11: Censoring rules for LRC.	56
Table 12: Analyses for LRC	56
Table 13: Analyses for DoR	59
Table 14: Analyses for TDM	62
Table 15: Scoring method for EORTC questionnaires	75
Table 16: EORTC QLQ-C30 definition of subscores	80
Table 17: EORTC QLQ-H&N35 definition of subscores	82
Table 18: NCI-CTC gradable parameters	86
Table 19: NCI-CTC non-gradable parameters	87
Table 20: Treatment-Emergent AESIs (Potential Tier 1 Safety Topics)	89

CCI

2 List of Abbreviations and Definition of Terms

A-P Anatomopathological ADaM Analysis Data Model

AE Adverse Event

AECI Adverse Events of Clinical Importance

AESI Adverse Event of Special Interest

AJCC American Joint Committee on Cancer

ALT Alanine Aminotransferase

AST Aspartate Aminotransferase

ALP Alkaline Phosphatase

ATC Anatomical Therapeutic Chemical Classification

BIRC Blinded Independent Review Committee

BMI Body Mass Index

BSA Body Surface Area

CI Confidence Interval

CCI

cIPD Clinically Important Protocol Deviations

CR Complete Response

CRR Complete Response Rate

CRO Contract Research Organization

CRT ChemoRadioTherapy
CSR Clinical Study Report

CSR Clinical Study Re CT ChemoTherapy

CxDy Cycle x Day y

DFT On-Study Duration of Feeding Tube Procedures

DoR Duration of Response

ECG Electrocardiogram

ECOG-PS Eastern Cooperative Oncology Group Performance Status

eCRF Electronic Case Report Form

eDISH evaluation of Drug-Induced Serious Hepatotoxicity

Xevinapant TrilynX Debio 1143-SCCHN-301/ MS202359 0006

EFS Event-Free Survival

eGFR estimated Glomerular Filtration Rate

END Elective Neck Dissection

EORTC European Organization for Research and Treatment of Cancer

EOT End Of Treatment

EOS End Of Study

GHS Global Health Scale

HR Hazard Ratio

HRQL Health-Related Quality of Life

HRU Health Resource Utilization

HSU Health State Utilities

IAP Integrated Analysis Plan
ICF Informed Consent Form

ICH International Council for Harmonisation of Technical Requirements for

Pharmaceuticals for Human Use

IDMC Independent Data Monitoring Committee

IPD Important Protocol Deviation

IMRT Intensity Modulated Radio Therapy

IQWIG Institut für Qualität und Wirtschaftlichkeit im Gesundheitswesen

IRT Integrated Randomization Technology

ITT Intent-to-treat

IWRS Interactive Web Response System

KM Kaplan-Meier

LA-SCCHN Locally Advanced Squamous Cell Carcinoma of the Head and Neck

LRC Locoregional Control
MAR Missing At Random

MedDRA Medical Dictionary for Regulatory Activities

MID Minimal Important Differences

NAT New Anticancer Treatment

NCI-CTCAE National Cancer Institute Common Terminology Criteria for Adverse Events

OIS Overall Imbalance Score

OR Objective Response

Xevinapant TrilynX Debio 1143-SCCHN-301/ MS202359 0006

ORR Objective Response Rate

OS Overall Survival

PD Progressive Disease

PFS Progression-Free Survival

CC

PR Partial Response
PT Preferred Term
QoL Quality of Life

QTcF QT interval corrected using Fridericia's formula RECIST Response Evaluation Criteria in Solid Tumors

RS Raw Score

RTF Rich Text Format

SAE Serious Adverse Event

SAF Safety

SD Standard Deviation

SD Stable Disease

SDTM Study Data Tabulation Model

SI Standard International System of Units

SMQ Standardized MedDRA Queries

SOC System Organ Class

TDM Time to Distant Metastasis

TEAE Treatment Emergent Adverse Event

TFTI Time to Feeding Tube Insertion

TRAE Treatment-Related Adverse Event

ULN Upper Limit of Normal VAS Visual Analogue Scale

WHO-DD World Health Organization Drug Dictionary

CCI

Modification History

Unique Identifier for Version	Date of IAP Version	Author	Changes from the Previous Version
1.0	25 OCT 2022	FFD	n.a.
2.0	27 OCT 2022		Administrative changes (title page)
3.0	07 DEC 2023		Implementation of health authority feedback and adding clarifying languages for the cut-off date determination of the interim and primary analysis. Adding new analyses or details to existing analyses following country-specific and general submission requirements (feeding tube, cIPD, Time to CR, AESI,
4.0	08 DEC 2023		Administrative changes (Links in 15.2.3.1). Some editorial changes.
5.0	07 MAR 2024		Update of the sequence of analyses (IAP section 6) according to the Clinical Study Protocol Version 12.0

4 Purpose of the Integrated Analysis Plan

The purpose of this integrated analysis plan (IAP) is to document technical and detailed specifications for all the planned analyses of data collected for protocol Debio 1143-SCCHN-301 / MS202359_0006. Results of the analyses described in this IAP will be included in the Clinical Study Report (CSR), except when otherwise stated. Additionally, the planned analyses identified in this IAP may be included in regulatory submissions or future manuscripts. Any post-hoc, or unplanned analyses performed to provide results for inclusion in the CSR but not identified in this prospective IAP will be clearly identified in the CSR. Candidate predictive biomarkers will be analyzed exploratory only and described in a separate analysis plan.

The IAP is based upon Section 10 (Statistical Considerations) of the study protocol dated 11-April-2023/version 10.0 and is prepared in compliance with the International Council for Harmonization of Technical Requirements for Pharmaceuticals for Human Use (ICH) E9.

Details on outputs used to support review of the study by an external Independent Data Monitoring Committee (IDMC) are available in the IDMC TFL shell document and further detail planning included in the IDMC charter 13-Jun-2022 / version 3.0.

The wording used in this IAP is chosen to best match the respective wording in the study protocol template, the Clinical Study Report (CSR) template, CDISC requirements and special requirements for table layouts. Therefore, the following approach is used:

Generally, the term 'participant' will be used instead of 'subject' or 'patient'. However, in tables and listings the term 'subject' will be used to match CDISC requirements, except for in-text tables where 'participant' will be used to match the CSR and protocol templates. Similarly, the term

'study intervention' and 'study treatment' will be used synonymously in this document, tables and listings will use 'treatment' for brevity reasons.

5 Objectives and Endpoints

The objectives and corresponding endpoints are presented in Table 1.

[figure not shown]
Table 1: Objectives, endpoints and statistical considerations

Objectives	Endpoints	Hypothesis	Primary Analysis Population	Timeframe/Time Point
Primary				
To demonstrate superior efficacy of xevinapant vs placebo when added to chemoradiotherapy (CRT) in locally advanced squamous cell carcinoma of the head and neck (LA-SCCHN)	Event-free survival (EFS) as assessed by the Blinded Independent Review Committee (BIRC) defined as the time from randomization to the first occurrence of any of the following events: • Death from any cause. • Progression: • Radiological, assessed per RECIST v1.1 or • Clinical, with or without RECIST v1.1-radiologically documented progression, assessed endoscopically. • Primary treatment failure before achieving a complete response (CR): requirement for radical salvage surgery that includes the primary tumor site, with documented viable tumor presenting anatomopathological findings even in the absence of formal RECIST v1.1 radiological progression. • Any radiological or clinical relapse after achieving a CR (locoregionally), including any event defined as locoregional treatment failure, even in the absence of formal radiological progressive disease confirmation: • Requirement for radical salvage surgery that includes the primary tumor site, regardless of anatomopathological findings or • Elective neck dissection or biopsy, with positive viable tumor cells on anatomopathological findings at 22 weeks or later after randomization. • Second cancers unless anatomopathological findings exclude squamous histology. Note: Investigator-assessed EFS will be used for supportive analysis.		Intent-to-treat	 From randomization to the earliest between any EFS event or end of study (EOS). Rate at 9, 12, 18, 24, 30 and 36-months post-randomization.

Objectives	Endpoints	Hypothesis	Primary Analysis Population	Timeframe/Time Point
Secondary				
To assess the efficacy of xevinapant compared to placebo when added to CRT according to additional efficacy endpoints	Overall survival (OS) defined as the time from randomization to death due to any cause.	Xevinapant prolongs OS in previously untreated patients with LA-SCCHN compared to matched placebo when administered in combination with platinum-based chemotherapy and IMRT.	Intent-to-treat	 From randomization to the earliest between death or EOS Rate at 12, 24, 36, 48 and 60 months post-randomization.
	Progression-free survival (PFS) according to RECIST v1.1 defined as the time from randomization to the first occurrence of progression (radiological or clinical, as assessed by the BIRC) or death from any cause. Note: Investigator-assessed PFS will be used for supportive analysis.	previously untreated patients with LA-SCCHN compared to matched placebo when administered in combination	Intent-to-treat	 From randomization to the earliest between PFS event or EOS. Rate at 9, 12,18, 24, 36, 48 and 60 months post-randomization.
	Locoregional control (LRC) defined as the time from randomization to the first occurrence of progression at the site of the primary tumor or the locoregional lymph nodes, either according to RECIST v1.1 or based on clinical assessment (radiological or clinical, as assessed by the Investigator). Note: Will be investigated by BIRC as supportive analysis.	previously untreated patients	Intent-to-treat	 From randomization to the earliest between PFS event or EOS. Rate at 9, 12, 18, 24, 36, 48 and 60 months post-randomization.
	Objective response rate (ORR), defined as the proportion of subjects with CR or partial response by RECIST v1.1, as assessed by the BIRC. Note: Investigator-assessed response will be used for supportive analysis.	in previously untreated patients with LA-SCCHN compared to matched placebo when	Intent-to-treat	- From randomization to the earliest between progression, start of a new anticancer therapy for this disease or participant EOS Rate at 9 and 12 months post-randomization.

Objectives	Endpoints	Hypothesis	Primary Analysis Population	Timeframe/Time Point
	CR rate (CRR) defined as the proportion of participants with CR by RECIST v1.1, as assessed by the BIRC. Note: Investigator-assessed response will be used for supportive analysis.	in previously untreated patients with LA-SCCHN compared to	Intent-to-treat	 From randomization to the earliest between progression, start of a new anticancer therapy for this disease or subject EOS. Rate at 9 and 12 months post-randomization.
	Duration of response (DoR) defined as the time from the first evidence of response (partial or complete, as assessed by the BIRC according to RECIST v1.1) to the first occurrence of progression (radiological or clinical, as assessed by the BIRC) or death from any cause. Note: Investigator-assessed DoR will be used for supportive analysis.	previously untreated participants with LA-SCCHN compared to matched placebo when administered in combination with platinum-	Intent-to-treat	 From first evidence of response (partial or complete) to the earliest between DoR event or EOS. Rate at 6, 12 and 24 months post first evidence of response.
	Proportion of participants with radical salvage surgery (excluding elective neck dissection without anatomopathological evidence of residual malignant cells).		Intent-to-treat	 From randomization to the earliest between radical salvage surgery or EOS. Rate at 9, 12, 18, 24, 36, 48 and 60 months post-randomization.
	Time to subsequent systemic cancer treatment.		Intent-to-treat	 From randomization to EOS Rate at 12, 18, 24, 36, 48 and 60 months post-randomization.

Objectives	Endpoints	Hypothesis	Primary Analysis Population	Timeframe/Time Point
To compare safety, tolerability and treatment compliance of xevinapant vs placebo, when added to CRT	Incidence and severity of adverse events (AE), serious adverse events and adverse events of special interest, changes in laboratory values, vital signs, and electrocardiograms according to NCI-CTCAE v 5.0.		Safety	• From signed informed consent to EOS.
	Extent of exposure of the different treatment agents (i.e., xevinapant or matched placebo, radiotherapy, chemotherapy) including: Treatment duration. Number of cycles. Actual dose. Dose intensity. Relative dose intensity. Incidence of treatment interruption. Incidence of treatment reduction. Incidence of treatment discontinuation.		Safety	• From first study treatment dose to EOT.
To compare the health-related quality of life of xevinapant vs placebo when added to CRT using patient-reported outcome questionnaires	-	Xevinapant is non-inferior for Global Health Scale /Quality of Life, Fatigue, Swallowing and Pain at Month 12 post-randomization in previously untreated patients with LA-SCCHN compared to matched placebo when administered in combination with platinumbased chemotherapy and IMRT.	Intent-to-treat	 From randomization to EOS. At baseline, Study Week 10, 20 and months 7, 12, 24, 36, 48 and 60 post-randomization.

6 Overview of Planned Analyses

This IAP covers the analyses based on the data cut-off dates for the interim analyses, the primary analysis, and the final analysis. Statistical analyses will be performed using cleaned eCRF data as well as external data. All data will be included up to a data cut-off date which is determined by the number of events for EFS/OS required for the analysis. Refer to Table 2 for the respective timing of the analyses.

Table 2: Planned Efficacy Analyses and Expected Timing

		Assumed	LAPCCICO					
Analysis	Events (IF)	Arm A	Arm B	month ^a after FPI	Notes			
EFS IA1	279 (65%)			30				
EFS IA2	365 (85%)	23.3		37	skipped if H_0^{EFS} could be rejected at EFS IA1			
EFS PA	429 (100%)			44	skipped if H_0^{EFS} could be rejected at EFS IA1 or EFS IA2			
OS IA1	154 (40%)			30	only if H_0^{EFS} could be rejected			
OS IA2	216 (56%)		37				37	only if H_0^{EFS} could be rejected, but not H_0^{OS} at OS IA1
OS IA3	270 (70%)	49.3		44	only if H_0^{EFS} could be rejected, but not H_0^{OS} at OS IA1 or OS IA2			
OS IA4	309 (80%)			50	only if H_0^{EFS} could be rejected, but not H_0^{OS} at OS IA1, IA2 or IA3			
OS FA	386 (100%)			65	only if H_0^{EFS} could be rejected, but not H_0^{OS} at OS IA1, IA2, IA3 or IA4			

Abbreviations: **EFS**: event-free survival, **FPI**: date of first participant randomized; **IA**: interim analysis; **IF**: information fraction; **OS**: overall survival; **PA**: primary analysis.

Analyses will be combined by using the same data cut-off date for EFS IA1/OS IA1, EFS IA2/OS IA2 as well as for EFS PA/OS IA3, which will be triggered by the respective numbers of EFS events as mentioned above or maximum additional follow-up time (refer IAP section 6.2), while the significance boundaries are adjusted accordingly to control the family-wise error rate (FWER) at 2.5% one-sided. However, in case the null hypothesis for EFS can already be rejected at an EFS interim analysis (IA) and the Sponsor decides to unblind the study, confirmatory analysis of EFS is completed with the respective EFS IA, and any further OS IA will be triggered by the number of OS events. In case the subsequent interim efficacy analyses will be triggered by the number of OS events as given in Table 2, it will be ensured to have an addition of at least 39 OS events to the

^a Based on exponential distributions using given medians for both arms and a 22-month-recruitment-period.

event count of the previous interim analysis (about 10% increase in information fraction) but not later than 12 months after the previous interim analysis cut-off date.

A hierarchical testing procedure will be used to test first primary null hypothesis H₀^{EFS} in a group sequential design, which uses alpha-spending according to Lan-DeMets with O'Brian-Fleming-like boundaries planning for a total number of 429 EFS events at primary analysis. If and only if that can be rejected either on interim or primary analysis, the null hypothesis H₀^{OS} will be confirmatory tested in a group sequential design with interim analysis as planned in Table 2, which uses alpha-spending according to Lan-DeMets with O'Brien Fleming-like boundaries planning for a total number of 386 OS events at final analysis. Table 3 shows the operating characteristics and decision boundaries for the confirmatory interim and primary/final analyses as planned.

Table 3: Operating Characteristics and Power Estimations

		Boundaries (HR) Boundaries (P-value)		Local			
Analysis	Events (IF)	Efficacy	Futility	Efficacy	Futility	Power ^a	Power ^a
EFS IA1	279 (65%)	0.737	0.886	0.005	0.163	53.3%	
EFS IA2	365 (85%)	0.793	-	0.013	-	25.8%	_
EFS PA	429 (100%)	0.821	0.821	0.020	0.020	9.1%	88.2%
OS IA1	154 (40%)	0.583	-	0.0004	-	5.7%	
OS IA2	216 (56%)	0.684	-	0.003	-	19.4%	_
OS IA3	270 (70%)	0.739	-	0.007	-	21.1%	
OS IA4	309 (80%)	0.767	-	0.010	-	13.5%	
OS FA	386 (100%)	0.813	0.813	0.021	0.021	19.9%	79.6%

Abbreviations: EFS: event-free survival; **HR**: hazard ratio; **IA**: interim analysis; **IF**: information fraction; **OS**: overall survival; **PA**: primary analysis.

Note: Decisions will be based on p-values with respect to actual number of events. Expected HRs under the assumption of an exponential distribution are only given as further information.

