6.1 Safety Monitoring Analysis

The IDMC will review quarterly descriptive summaries of accumulating participants' disposition and safety. The analyses will be conducted by unblinded supporting staff independent from the study team. The investigators/site personnel, CRO and sponsor team will remain blinded, except for a dedicated unblinded statistical team at the CRO that is preparing analyses for the IDMC.

The primary intent of these analyses is the patient safety monitoring. IDMC may recommend change or early stop of the study in case of safety issue.

Details on outputs used to support the review by the IDMC are available in the IDMC TFL shell document.

^a Power estimations are based on an assumed HR=0.73 for EFS and a HR=0.75 for OS and the prerequisite that the EFS null hypothesis can be rejected at either IA or PA. Futility-bounds are non-binding.

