6.2 Interim Analyses

A first interim analysis is planned once 279 EFS events as assessed by the BIRC (65% of EFS events required for the primary analysis) across both arms are observed. The number of EFS events as assessed by the BIRC will be monitored throughout the study. The cutoff date will be determined prospectively based on an event projection as the date when approximately 279 events will be reached. In case it turns out at the time of the EFS IA1 database lock that the observed number of EFS events is >3.5% below the planned number (<270), the IA cut-off date will be revised prior to the conduct of the analysis, based on blinded information on the number of EFS events only, to include at least 270 events in the IA dataset. The second interim analysis will be triggered once 85% of the total number of events (365 events) are observed or one year after the first interim analysis, whichever occurs first. The corresponding cutoff date will be re-evaluated based on event projections.

The interim analyses will be conducted for the IDMC by unblinded supporting staff independent from the study team and will focus on primary and selected secondary efficacy endpoint analyses. The Investigators/site personnel, Sponsor team and CRO will remain blinded, except for a dedicated unblinded statistical team at the CRO that is preparing analyses for the IDMC.

The main intent of these analyses is to demonstrate that xevinapant + CRT prolongs EFS as assessed by the BIRC versus placebo + CRT. No early stopping for superiority of efficacy is planned. Provided that EFS interim analysis results are positive, the data might be used for regulatory and health technology assessment submission purposes, in case of which the CRO and Sponsor team may be unblinded. Productions of outputs related to the analyses of the exploratory endpoints will be done only in case of positive recommendation from the IDMC, as needed. The IDMC will first share recommendation(s) based on the results of the interim efficacy analyses to the Firewall Team and jointly discuss results, as needed, for final Sponsor decision of unblinding according to the protocol, keeping all individuals involved in the study conduct blinded to preserve its integrity. If the study is futile or if EFS is detrimental at the IA, IDMC may recommend early stop of the study providing an observed lack of efficacy and/or futility putting the patients at risk when continuing the study.

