For the primary efficacy endpoint, a group-sequential design with α -spending according to Lan-DeMets with O'Brian-Fleming-like boundaries will be used to control the type I error rate. The observed number of EFS events as assessed by the BIRC at the time of the interim analysis will be used to recalculate the exact efficacy and futility boundaries to be used for the interim analysis as well as for the primary analysis (see also Table 3).

If the null hypothesis H_0^{EFS} of the primary efficacy endpoint EFS can be rejected, the null hypothesis H_0^{OS} of the secondary efficacy endpoint OS will be confirmatory tested by a group-sequential design with α -spending according to Lan-DeMets with O'Brian-Fleming-like boundaries to control for the type I error rate. The observed number of OS events at the time of the interim analysis will be used to recalculate the exact efficacy boundaries to be used for this interim analysis as well as for the further planned analyses (see also Table 3).

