14.1.1 Primary Analysis of the Primary Efficacy Endpoint EFS

The primary efficacy analysis will assess the difference in EFS between treatment arms using a one-sided stratified log-rank test. The significance boundaries are adjusted accordingly to control the family-wise error rate (FWER) at 2.5% one-sided (see also IAP Table 3). The stratification factors are tumor size (T4 vs other) and lymph node involvement (N0-1 vs N2 vs N3). These factors were chosen among the stratification factors for randomization to avoid issues caused by very small sample stratum sizes.

A Cox-proportional hazard regression model adjusted for the randomization factors will be used on the EFS with primary censoring rule (Table 4) to derive the hazard ratio and 95% CI between the 2 randomized regimens. In addition, a two-sided repeated CI (RCI) for the hazard ratio will be reported (Jennison and Turnbull, 2000), to account for the group sequential design in the confirmatory analyses (interim and primary analysis, as applicable). Ties will be handled by replacing the proportional hazards model by the discrete logistic model. The stratification factors used for the randomization of participants will be inserted as covariates in the regression model. EFS with sensitivity censoring rules will be analyzed with the same approach.

A further estimate of the hazard ratio (including 95% confidence interval) will be calculated based on the Cox proportional hazards model stratified by the stratification factors tumor size (T4 vs other) and lymph node involvement (N0-1 vs N2 vs N3). Each stratum will define separate

baseline hazard functions. Ties will be handled by replacing the proportional hazards model by the discrete logistic model.

The null and alternative hypotheses can be described in terms of hazard ratios as:

$$H_0^{EFS}$$
: $\lambda_{(xevinapant + CRT)} / \lambda_{(placebo + CRT)} \ge 1$ versus

$$H_1^{EFS}$$
: $\lambda_{(xevinapant + CRT)} / \lambda_{(placebo + CRT)} < 1$,

where $\lambda_{(xevinapant + CRT)}$, $\lambda_{(placebo + CRT)}$ represents the hazard of EFS for the (xevinapant + CRT) and the (placebo + CRT) group respectively.

The SAS code for the stratified log-rank test and the Cox-proportional hazard regression model is specified in Appendix 6

The proportional hazards assumption for the analysis of EFS will be examined using graphical methods by means of log-log-Survival plots (log(-log(S(t)))) vs log(time) by treatment arm, plots=(lls) in PROC LIFETEST.)

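### SAP Table 3, EFS IA1 row: the futility hazard ratio 0.886 and futility p-value 0.163 do not correspond at 279 events

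*SAP*

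**What the plan says.** SAP Section 6 introduces the table in these words: "Table 3 shows the operating characteristics and decision boundaries for the confirmatory interim and primary/final analyses as planned". The row at issue reads "EFS IA1 279 (65%) 0.737 0.886 0.005 0.163 53.3". In column order this is the number of events with its information fraction, the efficacy and futility boundaries as hazard ratios, the efficacy and futility boundaries as p-values, and the local power in percent.

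The note below the table says "Decisions will be based on p-values with respect to actual number of events" and adds "Expected HRs under the assumption of an exponential distribution are only given as further information". Footnote a states "Futility-bounds are non-binding".

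SAP Section 6.2 says that the "IDMC may recommend early stop of the study providing an observed lack of efficacy and/or futility", and that the observed number of BIRC-assessed EFS events "will be used to recalculate the exact efficacy and futility boundaries to be used for the interim analysis" and for the primary analysis.

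**The concern.** A boundary printed on two scales in one row should be one boundary. At a given event count and 1:1 allocation, a log-rank p-value and its approximate hazard ratio convert into each other, and the rest of Table 3 follows that conversion. The futility pair at EFS IA1 does not.

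This row holds the only interim futility boundary in the table. If the p-value is wrong, the planned threshold is wrong on the scale that decides. If the HR is wrong, its translation for the reader is wrong. In either case, anyone comparing the recalculated boundary with the plan meets two planned values. For example, a log-rank p of 0.160 at exactly 279 events would cross into futility by the HR entry and would not by the p entry.

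**Working it through.** **Inputs.** Events, HR boundaries, p-value boundaries and powers are from SAP Table 3. The 1:1 allocation is from Protocol Section 6.3. The one-sided 2.5% level and Lan-DeMets spending of O'Brien-Fleming type are from SAP Section 6. The assumed EFS HR of 0.73 is from Table 3, footnote a.

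**Formula.** z = −ln(HR) × √D / 2, with one-sided p = 1 − Φ(z). In the other direction, HR = exp(−2z / √D).

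**Step 1: does the formula reproduce the table?** The efficacy pairs:

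| Analysis | Events | Printed HR | p from HR | Printed p |
|---|---|---|---|---|
| EFS IA1 | 279 | 0.737 | 0.0054 | 0.005 |
| EFS IA2 | 365 | 0.793 | 0.0134 | 0.013 |
| EFS PA | 429 | 0.821 | 0.0202–0.0209 | 0.020 |
| OS IA1 | 154 | 0.583 | 0.00041 | 0.0004 |
| OS IA2 | 216 | 0.684 | 0.0026 | 0.003 |
| OS IA3 | 270 | 0.739 | 0.0064–0.0066 | 0.007 |
| OS IA4 | 309 | 0.767 | 0.0099 | 0.010 |
| OS FA | 386 | 0.813 | 0.0210 | 0.021 |

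All eight agree once rounding of both entries is allowed for. Ranges are shown where the agreement depends on it. The EFS PA and OS FA futility pairs repeat their efficacy pairs and so agree too. Solving the spending function directly for looks at 279, 365 and 429 events gives z = 2.546, 2.213 and 2.049, that is HR 0.737, 0.793 and 0.821, matching the printed EFS efficacy boundaries.

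**Step 2: the EFS IA1 futility pair, D = 279.** √279 / 2 = 8.352.

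- From the HR: z = 0.1210 × 8.352 = 1.011, so p = 0.156. Any HR that rounds to 0.886 (0.8855 to 0.8865) gives p between 0.1549 and 0.1572.
- From the p-value: p = 0.163 means z = 0.982, so HR = exp(−0.982 / 8.352) = 0.889. Any p that rounds to 0.163 (0.1625 to 0.1635) gives HR between 0.8888 and 0.8893.

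The intervals do not overlap. On the p scale their nearest edges are 0.1625 − 0.1572 = 0.005 apart, about five units of the last printed digit.

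**Step 3: would another convention explain it?** For HR 0.886:

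- Freedman's formula: 0.156
- a linear 1 − HR approximation: 0.171
- a 45:55 split of events: 0.157
- a 40:60 split of events: 0.161
- 270 events, the minimum that Section 6.2 accepts for this analysis: 0.160
- a two-sided p-value: 0.312

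None gives 0.163. That value would need about 263 events.

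**Step 4: which entry do the printed powers support?** Power at HR 0.73, with futility at IA1 honoured:

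| Futility boundary | IA1 | IA2 | PA | Total |
|---|---|---|---|---|
| HR 0.886 | 53.3% | 25.8% | 9.1% | 88.2% |
| p 0.163 | 53.3% | 25.8% | 9.2% | 88.3% |
| Printed in Table 3 | 53.3% | 25.8% | 9.1% | 88.2% |

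Without any futility stop the total would be 89.6%, so the printed power does assume one.

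**Step 5: size of the difference.** Probability of a futility signal at 279 events, Φ(z_bound − z_true):

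| True HR | Boundary HR 0.886 | Boundary p 0.163 |
|---|---|---|
| 0.73 | 5.3% | 5.0% |
| 0.80 | 19.7% | 18.9% |
| 1.00 | 84.4% | 83.7% |

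**The case against.** The strongest reply is that nothing turns on the printed cell. The HR column is declared informational, the futility bound is non-binding, the committee may only recommend stopping, and the exact boundary is recalculated from the observed events. The reported hazard ratio will not come from the log-rank test in any case: "A Cox-proportional hazard regression model adjusted for the randomization factors will be used on the EFS with primary censoring rule". Recalculation also needs the futility rule rather than the printed figure. That rule is not stated in the visible text, and the protocol's counterpart table (Table 10-9) is not shown in the public copy. All of this stands. It limits the point to a table correction, but it does not make the two entries agree.

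A second reply is that the powers already identify the culprit. Across the rounding range, a boundary at HR 0.886 gives a total of 88.15% to 88.20%, while one at p 0.163 gives 88.29% to 88.31%, so the printed 88.2% (and the 9.1%) favour the HR. Keeping p 0.163 would mean that three printed cells are wrong rather than one. This makes 0.886 with 0.156 the likelier correction. It is still an inference from a 0.1-point difference in approximate power, with the futility rule unseen. A p of 0.163 is also a 5.0% futility probability under HR 0.73, which could have been a design target, although the documents do not say so.

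Finally, the ten agreeing pairs are only eight distinct checks, and several p-values are printed to one significant digit. That is fair. The efficacy pair in the same 279-event row still fits.

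**Conclusion.** The point holds as a minor correction. The EFS IA1 futility HR and p-value in SAP Table 3 differ by 0.007 on the p scale and 0.003 on the HR scale, and rounding does not account for it. One entry is wrong as printed. The p-value is the more likely one, but the documents do not prove it.

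The consequence is small: under one percentage point in the chance of a futility signal across true HRs from 0.73 to 1, and about 0.1 point in total EFS power. Type I error, efficacy boundaries and event counts do not change.

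The result rests on 1:1 allocation and the usual large-sample link between the log-rank statistic and the hazard ratio, which the rest of the table follows. The power comparison also assumes that futility stopping at IA1 is honoured.

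**What to change.** Check the EFS IA1 futility boundary against the design software output and print one consistent pair.

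- If the HR is right: 0.886 with p 0.156 (the unrounded HR could move the third decimal to 0.155 or 0.157), and the powers stay as printed.
- If the p-value is right: 0.889 with p 0.163, EFS PA local power restated as 9.2% and total EFS power as 88.3%.

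The cost is one table cell, or one cell plus two power figures. Events, alpha, efficacy boundaries and patients are not affected.
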